7.1.3. Discontinuation of Inadvertently Enrolled Patients

If the sponsor or investigator identify a patient who did not meet enrollment criteria and was inadvertently enrolled, a discussion must occur between the sponsor CRP and the investigator to determine if the patient may continue in the study. If both agree it is medically appropriate to continue, the investigator must obtain documented approval from the sponsor CRP to allow the inadvertently enrolled patient to continue in the study with or without treatment with investigational product.

7.1.4. Patients Lost to Follow-Up

Site personnel are expected to make diligent attempts to contact patients who fail to return for a scheduled visit or were otherwise unable to be followed up by the site. A patient will be considered lost to follow-up if he or she repeatedly fails to return for scheduled visits and is unable to be contacted by the study site.

8. Study Assessments and Procedures

[Appendix 2](#) lists the Schedule of Activities, with the study procedures and their timing (including tolerance limits for timing).

[Appendix 3](#) lists the laboratory tests that will be performed for this study.

Unless otherwise stated in the subsections below, all samples collected for specified laboratory tests will be destroyed within 60 days of receipt of confirmed test results. Certain samples may be retained for a longer period, if necessary, to comply with applicable laws, regulations, or laboratory certification standards.

8.1. Efficacy Assessments

8.1.1. Primary Efficacy Assessment Scale

8.1.1.1. SLEDAI-2K

The SLEDAI-2K is a validated global disease activity instrument that focuses on high-impact disease manifestations across 9 organ systems. It includes 24 clinical and laboratory variables with manifestations graded by the affected organ system. CNS: Seizure, Psychosis, Organic Brain Syndrome, Visual Disturbance, Cranial Nerve Disorder, Lupus Headache, CVA; Vascular: Vasculitis; Musculoskeletal: Arthritis, Myositis; Renal: Urinary Casts, Hematuria, Proteinuria, Pyuria; Mucocutaneous: Rash, Alopecia, Mucosal Ulcers; Cardiovascular and Respiratory: Pleurisy, Pericarditis; Immunologic: Low complement, Increased DNA Binding; Constitutional: Fever; Hematologic: Thrombocytopenia, Leukopenia. The primary endpoint in this study will assess remission of arthritis and/or rash as defined by the SLEDAI-2K.

8.1.2. Secondary Efficacy and Exploratory Assessments

8.1.2.1. SLE Responder Index-4 (SRI-4)

The SRI-4 is a composite index used to assess disease activity in SLE. The SLEDAI-2K component is used to capture clinically meaningful improvement in disease activity, while the BILAG and Physician's Global Assessment of Disease Activity components ensure that the improvement in overall disease is not accompanied by disease worsening in other organ systems. SRI-4 response is defined as:

- Reduction of ≥ 4 points from baseline in SLEDAI-2K score;
- No new BILAG A or no more than 1 new BILAG B disease activity scores; and
- No worsening (defined as an increase of ≥ 0.3 points [10 mm] from baseline) in Physician's Global Assessment of Disease Activity.

8.1.2.2. Physician's Global Assessment of Disease Activity

The Physician's Global Assessment of Disease Activity is the physician's assessment of the patient's overall disease activity due to SLE, as compared with all possible patients with SLE. The Physician's Global Assessment of Disease Activity is scored using a 100 mm visual analog scale (VAS), where 0 mm (measured from the left starting point of the line) indicates no disease

activity and 100 mm (measured from the left starting point of the line) indicates the most severe disease activity possible for all patients with SLE (or death). The Physician's Global Assessment of Disease Activity score is indicated by making a vertical tick mark on the line between 0 and 100 mm. There are benchmarks of 0 (0 mm), 1 (33 mm), 2 (67 mm), and 3 (100 mm) on the line corresponding to no, mild, moderate, and severe SLE disease activity, respectively.

8.1.2.3. BILAG2004

The BILAG2004 index is a validated global disease activity index designed on the basis of the physician's intention to treat (ITT), focusing on changes in disease manifestations (not present, improving, same, worse, or new) occurring in the last 4 weeks compared with the previous 4 weeks. The instrument assesses 97 clinical signs, symptoms, and laboratory parameters across 9 organ system domains: constitutional, mucocutaneous, neuropsychiatric, musculoskeletal, cardiorespiratory, gastrointestinal, ophthalmic, renal, and hematology. A BILAG A disease activity score is severe disease activity requiring high-dose oral or IV corticosteroids, immunomodulators, or high-dose anticoagulation along with high-dose corticosteroids or immunomodulators. A BILAG B disease activity score is moderate disease activity requiring low-dose oral corticosteroids, intramuscular or intra-articular corticosteroid injections, topical corticosteroids or immunomodulators, antimalarials, or symptomatic therapy. BILAG C corresponds to stable mild disease, BILAG D is inactive disease that was active previously, and BILAG E indicates the system was never involved.

8.1.2.4. 28 Tender Joint Count & 28 Swollen Joint Count

The 28 joints to be examined and assessed as tender or not tender for tender joint count and as swollen or not swollen for swollen joint count include 14 joints on each side of the patient's body: the 2 shoulders, the 2 elbows, the 2 wrists, the 10 metacarpophalangeal joints, the 2 interphalangeal joints of the thumb, the 8 proximal interphalangeal joints, and the 2 knees.

8.1.2.5. Cutaneous Lupus Erythematosus Disease Area and Severity Index (CLASI)

The CLASI is a validated scale used to assess cutaneous manifestations of SLE consisting of 2 scores. The first summarizes the activity of the disease while the second is a measure of the damage done by the disease. Activity is scored on the basis of erythema, scale/hyperkeratosis, mucous membrane involvement, acute hair loss, and nonscarring alopecia. Damage is scored in terms of dyspigmentation and scarring, including scarring alopecia.

8.1.2.6. SLEDAI Flare Index (SFI)

The SFI uses the SLEDAI-2K score, disease activity scenarios, treatment changes, and Physician's Global Assessment of Disease Activity to define mild/moderate and severe flares. The index takes into account the absolute change in total scores, new or worsening symptoms, and increases in medication use or hospitalization due to the disease activity.

8.1.2.7. SLICC/ACR Damage Index

The SLICC/ACR damage index is scored on 41 items representing damage to 12 organ systems. The index records damage occurring in patients with SLE regardless of its cause and includes specific comorbidities associated with SLE that may be due to treatment-related toxicity.

8.1.3. Appropriateness of Assessments

All assessments made in this study are standard, widely used, and generally recognized as reliable, accurate, and relevant.

8.2. Adverse Events

Investigators are responsible for monitoring the safety of patients who have entered this study and for alerting Lilly or its designee to any event that seems unusual, even if this event may be considered an unanticipated benefit to the patient.

The investigator is responsible for the appropriate medical care of patients during the study.

Investigators must document their review of each laboratory safety report.

The investigator remains responsible for following, through an appropriate health care option, AEs that are serious or otherwise medically important, considered related to the investigational product or the study, or that caused the patient to discontinue the investigational product before completing the study. The patient should be followed until the event resolves, stabilizes with appropriate diagnostic evaluation, or is reasonably explained. The frequency of follow-up evaluations of the AE is left to the discretion of the investigator.

Lack of drug effect is not an AE in clinical studies, because the purpose of the clinical study is to establish treatment effect.

After the ICF is signed, study site personnel will record via eCRF the occurrence and nature of each patient's preexisting conditions, except SLE, as it is the disease under treatment in the study. In addition, site personnel will record via eCRF any change in the condition(s) and any new conditions as AEs. Investigators should record their assessment of the potential relatedness of each AE to protocol procedure, studied disease state, and/or investigational product via eCRF.

The investigator will interpret and document whether or not an AE has a reasonable possibility of being related to study treatment, study device, or a study procedure, taking into account the disease, concomitant treatment or pathologies.

A "reasonable possibility" means that there is a cause and effect relationship between the investigational product, study device and/or study procedure and the AE.

The investigator answers yes/no when making this assessment.

Planned surgeries and nonsurgical interventions should not be reported as AEs unless the underlying medical condition has worsened during the course of the study.

If a patient's investigational product is discontinued as a result of an AE, study site personnel must report this to Lilly or its designee via eCRF, clarifying if possible, the circumstances leading to any dosage modifications, or discontinuations of treatment.

8.2.1. Serious Adverse Events

An SAE is any AE from this study that results in one of the following outcomes:

- death
- initial or prolonged inpatient hospitalization
- a life-threatening experience (that is, immediate risk of dying)
- persistent or significant disability/incapacity
- congenital anomaly/birth defect
- considered significant by the investigator for any other reason: important medical events that may not result in death, be life-threatening, or require hospitalization may be considered serious, based upon appropriate medical judgment

Although all AEs after signing the ICF are recorded in the eCRF, SAE reporting begins after the patient has signed the ICF and has received investigational product. However, if an SAE occurs after signing the ICF, but prior to receiving investigational product, it needs to be reported ONLY if it is considered reasonably possibly related to study procedure.

Study site personnel must alert Lilly or its designee of any SAE within 24 hours of investigator awareness of the event via a sponsor-approved method. If alerts are issued via telephone, they are to be immediately followed with official notification on study-specific SAE forms. This 24-hour notification requirement refers to the initial SAE information and all follow-up SAE information.

Pregnancy (during maternal or paternal exposure to investigational product) does not meet the definition of an AE. However, to fulfill regulatory requirements any pregnancy should be reported following the SAE process to collect data on the outcome for both mother and fetus.

Investigators are not obligated to actively seek AEs or SAEs in subjects once they have discontinued and/or completed the study (the patient summary eCRF has been completed). However, if the investigator learns of any SAE, including a death, at any time after a subject has been discharged from the study, and he/she considers the event reasonably possibly related to the study treatment or study participation, the investigator must promptly notify Lilly.

8.2.2. Adverse Events and Laboratory Tests of Special Interest (AESIs)

Adverse events of special interest (AESIs) or laboratory results of special interest will include severe or opportunistic infections; myelosuppressive events of anemia, leukopenia, neutropenia, lymphopenia, and thrombocytopenia; thrombocytosis; and elevations in ALT or AST (>3 x ULN) and total bilirubin (>2 x ULN).

8.2.2.1. Suspected Unexpected Serious Adverse Reactions

Suspected unexpected serious adverse reactions (SUSARs) are serious events that are not listed in the IB and that the investigator identifies as related to investigational product or procedure. United States 21 CFR 312.32 and European Union Clinical Trial Directive 2001/20/EC and the associated detailed guidances or national regulatory requirements in participating countries require the reporting of SUSARs. Lilly has procedures that will be followed for the recording

and expedited reporting of SUSARs that are consistent with global regulations and the associated detailed guidances.

8.2.2.2. Reasonably Anticipated Serious Adverse Events

In the SLE population, the occurrence of renal failure/nephropathy, major cerebrocardiovascular events (including cardiovascular—death, MI, hospitalization for unstable angina, hospitalization for heart failure, serious arrhythmia, resuscitated sudden death, cardiogenic shock due to MI, coronary revascularization procedure; neurologic—stroke; and peripheral vascular events), skeletal-related events (including osteoporosis), SLE flares, and serious infections are reasonably anticipated due to the disease state, comorbid conditions, and use of concomitant medications. The serious instances of these reasonably anticipated AEs will be reviewed in aggregate on a regular periodic basis to evaluate any numerical imbalances between treatment groups in SAEs for reporting to the Food and Drug Administration in the US.

8.2.3. Complaint Handling

Lilly collects product complaints on investigational products and drug delivery systems used in clinical studies in order to ensure the safety of study participants, monitor quality, and to facilitate process and product improvements.

Patients will be instructed to contact the investigator as soon as possible if he or she has a complaint or problem with the investigational product so that the situation can be assessed.

8.3. Treatment of Overdose

Refer to the IB.

8.4. Safety Assessments

8.4.1. Electrocardiograms

For each patient, 12-lead standard ECGs should be collected locally according to the Schedule of Activities ([Appendix 2](#)). Electrocardiograms may be obtained at additional times, when deemed clinically necessary.

Any clinically significant findings from ECGs that result in a diagnosis and that occur after the patient receives the first dose of the investigational treatment should be reported to Lilly or its designee as an AE via eCRF.

8.4.2. Vital Signs

For each patient, vital signs measurements should be conducted according to the Schedule of Activities ([Appendix 2](#)).

Any clinically significant findings from vital signs measurement that result in a diagnosis and that occur after the patient receives the first dose of investigation product should be reported to Lilly or its designee as an AE via eCRF.

8.4.3. Laboratory Tests

For each patient, laboratory tests detailed in (Appendix 3) should be conducted according to the Schedule of Activities (Appendix 2).

Any clinically significant findings from laboratory tests that result in a diagnosis and that occur after the patient receives the first dose of investigational product should be reported to Lilly or its designee as an AE via eCRF.

8.4.4. Hepatitis B Virus (HBV) DNA Monitoring

HBV DNA testing will be performed in enrolled patients who tested positive for HBcAb at screening. Patients who are HBcAb positive and HBV DNA negative (undetectable) at Visit 1 will require HBV DNA monitoring every 3 months and at the patient's last visit, regardless of their HBsAb status.

If the HBV DNA result is above the LLOQ, then the patient should be referred to a hepatology specialist immediately. In selected cases, investigators may temporarily continue investigation product in accordance with current immunomodulator management in the setting of HBV DNA positivity. This option may be considered in consultation with the sponsor (or its designee) and evaluation of individual patient risks and benefits.

If a single result of "target detected" is obtained (a result above the LLOQ), the test should be repeated within approximately 2 weeks. If the repeat test result is "target not detected," monitoring may resume according to the Schedule of Activities.

For study sites in Japan (or elsewhere if required), if a patient is HBcAb positive and/or HBsAb positive and negative for HBV DNA at Visit 1, HBV DNA needs to be checked at least monthly and at the patient's last visit.

8.4.5. Chest X-ray and Tuberculosis Testing

A posterior-anterior view chest x-ray will be obtained locally, unless results from a chest x-ray obtained within 6 months prior to the study are available. The chest x-ray will be reviewed by the investigator or his/her designee to exclude patients with active TB infection. In addition, patients will be tested at screening and entry for evidence of active or latent TB as described in the Exclusion Criteria (Section 5.2).

8.4.6. Quick Inventory of Depressive Symptomatology Self-Rated–16 (QIDS-SR₁₆)

The QIDS-SR₁₆ is a 16-item, self-report instrument intended to assess the existence and severity of symptoms of depression as listed in the American Psychiatric Association's *Diagnostic and Statistical Manual of Mental Disorders, 4th Edition* (APA 1994). Patients are asked to consider each statement as it relates to the way they have felt for the past 7 days. There is a 4-point scale for each item ranging from 0 to 3. The 16 items corresponding to 9 depression domains are summed to give a single score ranging from 0 to 27, with higher scores denoting greater symptom severity. The domains assessed by the instrument include: sad mood, concentration,

self-criticism, suicidal ideation, interest, energy/fatigue, sleep disturbance (initial, middle, and late insomnia or hypersomnia), decrease/increase in appetite/weight, and psychomotor agitation/retardation. Additional information and the QIDS-SR₁₆ questions may be found on the University of Pittsburgh Epidemiology Data Center web site (Inventory of Depressive Symptomatology/Quick Inventory of Depressive Symptomatology [WWW]) (Rush et al. 2003; Trivedi et al. 2004).

8.4.7. Safety Monitoring

Lilly will periodically review evolving aggregate safety data within the study by appropriate methods.

The Lilly CRP will monitor safety data throughout the course of the study. Lilly will review SAEs within time frames mandated by company procedures. The Lilly CRP will, as is appropriate, consult with the functionally independent Global Patient Safety (GPS) therapeutic area physician or clinical scientist and periodically review trends in safety data and laboratory analytes. Any concerning trends in frequency or severity noted by an investigator and/or Lilly or its designee may require further evaluation.

All deaths and SAE reports will be reviewed in a blinded manner by Lilly during the clinical trial. These reports will be reviewed to ensure completeness and accuracy but will not be unblinded to Lilly during the clinical trial. If a death or clinical AE is deemed serious, unexpected, and possibly related to investigational product, only Lilly GPS will be unblinded for regulatory reporting and safety monitoring purposes. These measures will preserve the integrity of the data collected during this trial and minimize any potential for bias while providing for appropriate safety monitoring.

If a study patient experiences elevated ALT ≥ 3 x ULN, ALP ≥ 2 x ULN, or elevated TBL ≥ 2 x ULN, clinical and laboratory monitoring should be initiated by the investigator. Details for hepatic monitoring depend upon the severity and persistence of observed laboratory test abnormalities. To ensure patient safety and comply with regulatory guidance, the investigator is to consult with the Lilly CRP regarding collection of specific recommended clinical information and follow-up laboratory tests (see [Appendix 4](#)).

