7.1. Discontinuation from Study Treatment

7.1.1. Interruption of Investigational Product

In some circumstances, it may be necessary to temporarily interrupt treatment as a result of AEs or abnormal laboratory values that may have an unclear relationship to investigational product. Except in cases of emergency, it is recommended that the investigator consult with Lilly (or its designee) before temporarily interrupting therapy for reasons other than those defined in [Table JAHH.3](#) below. Retest timing and frequency is at the investigator's discretion.

The investigator must obtain approval from Lilly (or its designee) before restarting investigational product that was temporarily discontinued because of an AE or abnormal laboratory value. Investigational product must be held in the following situations and may be resumed as noted in [Table JAHH.3](#).

Table JAHH.3. Criteria for Temporary Interruption of Investigational Product

Hold investigational product if the following laboratory test results occur:	Investigational product may be resumed after approval from Lilly (or its designee) when:
WBC count <2000 cells/ μ L (<2.00x10 ³ / μ L or <2.00 GI/L)	WBC count \geq 2500 cells/ μ L (\geq 2.50x10 ³ / μ L or \geq 2.50 GI/L)
ANC <1000 cells/ μ L (<1.00x10 ³ / μ L or <1.00 GI/L)	ANC \geq 1200 cells/ μ L (\geq 1.20x10 ³ / μ L or \geq 1.20 GI/L)
Lymphocyte count <500 cells/ μ L (<0.50x10 ³ / μ L or <0.50 GI/L) Note: IP can be continued with a lymphocyte count <500 cells/ μ L but \geq 300 cells/ μ L (<0.30x10 ³ / μ L or <0.30 GI/L) if the low lymphocyte count is considered by the investigator to be a result of the underlying SLE disease or concomitant medications. IP must be held for lymphocyte count <300 cells/ μ L, regardless of cause.	Lymphocyte count \geq 750 cells/ μ L (\geq 0.75x10 ³ / μ L or \geq 0.75 GI/L) Note: If IP is held for lymphocyte count <300 cells/ μ L, it may be resumed after approval from Lilly (or its designee) when the lymphocyte count is \geq 500 cells/ μ L if the low lymphocyte count is considered by the investigator to be a result of the underlying SLE disease or concomitant medications.
Platelet count <25,000/ μ L (<25x10 ³ / μ L or <25 GI/L)	Platelet count \geq 50,000/ μ L (\geq 50x10 ³ / μ L or \geq 50 GI/L)
eGFR <40 mL/min/1.73 m ² (from serum creatinine)	eGFR \geq 50 mL/min/1.73 m ²
ALT or AST >5 x ULN	ALT and AST return to <2 x ULN, and IP is not considered to be the cause of enzyme elevation

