Hemoglobin <8 g/dL (<80.0 g/L)	Hemoglobin \geq 9 g/dL (\geq 90.0 g/L)
Symptomatic herpes zoster	All skin lesions have crusted and are resolving
Severe infection that, in the opinion of the investigator, merits the IP being discontinued	Resolution of infection

Abbreviations: ALT = alanine aminotransferase; ANC = absolute neutrophil count; AST = aspartate aminotransferase; eGFR = estimated glomerular filtration rate; IP = investigational product; ULN = upper limit of normal; WBC = white blood cell.

7.1.2. *Permanent Discontinuation of Investigation Product*

Any patient who is permanently discontinued from investigational product for an AE or abnormal laboratory result should have the reason for investigational product discontinuation reported as the AE or abnormal laboratory value.

Discontinuation of the investigational product for abnormal liver tests **should be considered** by the investigator when a patient meets one of the following conditions after consultation with the Lilly designated medical monitor:

- ALT or AST >8 x ULN
- ALT or AST >5 x ULN for more than 2 weeks after temporary interruption of investigational product
- ALT or AST >3 x ULN and either total bilirubin level (TBL) >2 x ULN or INR >1.5 x ULN
- ALT or AST >3 x ULN with the appearance of fatigue, nausea, vomiting, right upper-quadrant pain or tenderness, fever, rash, and/or eosinophilia (>5%)
- alkaline phosphatase (ALP) >3 x ULN
- ALP >2.5 x ULN and TBL >2 x ULN
- ALP >2.5 x ULN with the appearance of fatigue, nausea, vomiting, right upper quadrant pain or tenderness, fever, rash, and/or eosinophilia (>5%).

Patients should be discontinued from the investigational product in the following circumstances:

- WBC count <1000 cells/ μ L ($1.00 \times 10^3 / \mu$ L or 1.00 GI/L)
- ANC <500 cells/ μ L ($0.50 \times 10^3 / \mu$ L or 0.50 GI/L)
- Lymphocyte count <200 cells/ μ L ($0.20 \times 10^3 / \mu$ L or 0.20 GI/L)
- Hemoglobin <6.5 g/dL (<65.0 g/L).

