For lab values that meet permanent discontinuation thresholds, investigational product should be discontinued unless, in the opinion of the investigator, the lab abnormality is due to intercurrent illness or another identified factor. After consultation with the Lilly-designated medical monitor, the patient may be able to continue receiving investigational product. Lab tests may be repeated within 1 week to confirm whether discontinuation criteria have been met. Furthermore, if investigational product is not discontinued due to intercurrent illness, the investigator must confirm the lab value no longer meets discontinuation thresholds following the resolution of the intercurrent illness or other identified factor.

In addition, patients will be discontinued from investigational product in the following circumstances:

- Pregnancy

- Malignancy (except for successfully treated basal cell or squamous epithelial skin cancers)
- HBV DNA above the lower limit of quantification (LLOQ)

Note: If the HBV DNA result is “target detected” (above the LLOQ), then the patient should be referred to a hepatology specialist immediately. In selected cases, investigators may temporarily continue investigational product in accordance with current immunomodulator management in the setting of HBV DNA positivity. This option may be considered in consultation with Lilly (or its designee) and evaluation of individual patient risks and benefits. Refer to Section 8.4.4 for additional instruction on HBV DNA monitoring.

Some possible reasons that may lead to permanent discontinuation include:

- Enrollment in any other clinical trial involving an investigational product or enrollment in any other type of medical research judged not to be scientifically or medically compatible with this study
- Participation in the study needs to be stopped for medical, safety, regulatory, or other reasons consistent with applicable laws, regulations, and good clinical practice (GCP)
- Investigator Decision
 - the investigator decides that the patient should be discontinued from the study

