- b Unscheduled blood chemistry (including CPK), hematology, and urinalysis panels may be performed at the discretion of the investigator. If tests are done to evaluate laboratory results to resume investigational product, samples must be assayed centrally.
- c eGFR for serum creatinine will be calculated by the central laboratory using the Modification of Diet in Renal Disease (MDRD) isotope dilution mass spectrometry traceable method.
- d Fasting laboratory values for glucose and lipids will be required at baseline, Week 12, and Week 24. If a patient attends these visits in a nonfasting state, this will not be considered a protocol violation. These tests may be performed nonfasting at all other visits.
- e Differential and blood smear may be performed if necessary.
- f Lipid panel consists of direct HDL-C, triglycerides, cholesterol, and LDL-C (calculation from Friedewald et al. 1972).
- g For all women of childbearing potential, a serum pregnancy test (central laboratory) will be performed at Visit 1, and both urine (local laboratory) and serum pregnancy (central laboratory) tests will be performed at Visit 2 to determine study eligibility. Urine pregnancy tests (local laboratory) will also be performed at each subsequent study visit per the Schedule of Activities.
- h To confirm postmenopausal status for women ≥ 40 and < 60 years of age, an FSH test will be performed. Nonchildbearing potential is defined as an FSH ≥ 40 mIU/mL and a cessation of menses for at least 12 months.
- i A positive hepatitis C antibody result will be confirmed with a positive hepatitis C virus result.
- j Microscopic examination of sediment will be performed if abnormalities are noted on the routine urinalysis.
- k HBV DNA testing will be performed in patients who tested positive for HBcAb at screening. Patients who are HBcAb positive and HBV DNA negative at Visit 1 will require HBV DNA monitoring every 3 months, at an early termination (ET) visit, and at Visit 801, regardless of their HBsAb status. If the HBV DNA result is above the lower limit of quantification (LLOQ), refer to Section 7.1.2 and Section 8.4.4. For study sites in Japan (or elsewhere if required), if a patient is HBcAb positive and/or HBsAb positive and negative for HBV DNA at Visit 1, HBV DNA needs to be checked at least monthly and at the patient's last visit.

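### The hepatic monitoring trigger in Protocol 8.4.7 omits AST, so an AST-led rise can meet a 7.1.2 discontinuation criterion without starting the 8.4.7 work-up

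*Protocol*

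**What the plan says.** Protocol 8.4.7 has the investigator begin clinical and laboratory monitoring under these conditions: "If a study patient experiences elevated ALT ≥ 3 x ULN, ALP ≥ 2 x ULN, or elevated TBL ≥ 2 x ULN". It then adds that "the investigator is to consult with the Lilly CRP regarding collection of specific recommended clinical information and follow-up laboratory tests", and refers to Appendix 4 for the tests.

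Section 7.1.2 lists the liver-test findings for which stopping drug should be considered. Four criteria rest on aminotransferases, and each names ALT or AST:

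- above 8 × ULN;
- above 5 × ULN for more than 2 weeks after a temporary interruption;
- above 3 × ULN with bilirubin above 2 × ULN or INR above 1.5 × ULN;
- above 3 × ULN with new symptoms (nausea, fatigue, fever and others) or eosinophilia above 5%.

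The investigator is to consider discontinuation "when a patient meets one of the following conditions after consultation with the Lilly designated medical monitor".

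The compulsory hold in Table JAHH.3 (section 7.1.1) applies at "ALT or AST >5 x ULN". Dosing may resume, with sponsor approval, once both enzymes are below 2 × ULN and the drug is not thought to be the cause.

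On retesting, 7.1.2 says: "Lab tests may be repeated within 1 week to confirm whether discontinuation criteria have been met". The same paragraph makes stopping the default for values at permanent-discontinuation thresholds, unless the investigator attributes them to another cause. If drug continues because of intercurrent illness, the investigator has to confirm afterwards that the value no longer meets the threshold.

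**The concern.** The protocol treats the two enzymes alike when it decides who may enter, when drug is held, when stopping is considered and what counts as a result of special interest. It separates them only when it says who gets the hepatic work-up, and it gives no reason. That work-up would inform the other decisions: whether the rise is hepatic, whether the drug is the cause, and whether to stop.

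At stake is even handling of liver signals. A patient with ALT at a given multiple is directed to monitoring. For a patient with AST at the same multiple and ALT below 3 × ULN, starting it is left to the investigator's discretion.

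**Working it through.** The plan states no figure to reproduce. The check is threshold logic, applied to the rules as written.

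**Step 1. Is 8.4.7 the exception?** Visible aminotransferase thresholds elsewhere: exclusion [19] (1), exclusion [60]a (1), the hold in Table JAHH.3 (1), its resume rule (1), the 7.1.2 criteria (4), and the special-interest lists in 8.2.2 and 9.2.6 (2). Total 1 + 1 + 1 + 1 + 4 + 2 = 10, and all 10 name both enzymes.

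**Step 2. Define an AST-led rise.** ALT < 3, ALP < 2 and bilirubin < 2 × ULN. All three 8.4.7 conditions are then false, whatever the AST value.

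**Step 3. Evaluate the rules.** In the AST rows the other liver tests are normal; the results are the same for any ALT below 3 × ULN. Values are multiples of ULN.

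| Case | 7.1.2 criterion met | Hold required | 8.4.7 as written | 8.4.7 with AST ≥ 3 added |
|---|---|---|---|---|
| AST 3.0, symptoms | no | no | no | yes |
| AST 3.1, 4.0 or 5.0, no symptoms, INR normal | no | no | no | yes |
| AST 3.1, 4.0 or 5.0, symptoms or eosinophilia | yes | no | no | yes |
| AST 3.1, 4.0 or 5.0, INR 1.6 | yes | no | no | yes |
| AST 5.1, symptoms | yes | yes | no | yes |
| AST 8.1, no symptoms | yes | yes | no | yes |
| ALT 4.0, symptoms (comparison) | yes | no | yes | yes |

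The band with a 7.1.2 criterion met but neither a required hold nor an 8.4.7 trigger is AST > 3 to 5 × ULN. The lower end is strict because 7.1.2 uses > 3; 5.0 is inside because the hold uses > 5.

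**Step 4. Go through the 7.1.2 criteria for an AST-led rise.**

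- Above 8 × ULN, or above 5 × ULN persisting after interruption: drug is already held.
- Above 3 × ULN with bilirubin above 2 × ULN: 8.4.7 starts through bilirubin.
- Above 3 × ULN with INR above 1.5 × ULN and bilirubin below 2 × ULN: uncovered up to 5 × ULN. INR is not in the Appendix 3 test list, so this criterion can be recognised only if extra tests are ordered, and 8.4.7 does not prompt them here.
- Above 3 × ULN with symptoms or eosinophilia: uncovered up to 5 × ULN.

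**Step 5. Can the gap be closed with data already collected?** Chemistry (with AST) and hematology (with eosinophils) are drawn at Visits 3 to 9, that is 9 − 3 + 1 = 7 post-baseline treatment visits. Section 8.2 adds: "Investigators must document their review of each laboratory safety report". Recognising an AST trigger needs no new scheduled sampling.

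**The case against.** The strongest reply is that such a patient is not left unattended, and most of it stands.

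- 7.1.2 brings in the sponsor's medical monitor.
- The default-to-stop and confirmation rules in 7.1.2 may reach this patient too. Their scope is arguable: they speak of values at permanent-discontinuation thresholds, while the liver list says only that stopping should be considered.
- Section 8.2 requires follow-up of adverse events that are serious, otherwise medically important or judged related, until they resolve, stabilise with diagnostic evaluation or are explained.
- Appendix 3 allows unscheduled panels, and 8.4.7 has the sponsor review laboratory trends.
- Above 5 × ULN the hold applies, and Appendix 3 says of retests before restarting: "If tests are done to evaluate laboratory results to resume investigational product, samples must be assayed centrally".

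A reader might infer that a patient with AST at 4 × ULN and nausea stays on drug with no review. The documents do not support that. No hold means only that Table JAHH.3 compels none; 7.1.1 leaves room for other interruptions, and 7.1.2 puts discontinuation on the table.

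It is also fair to say that 8.4.7 does not limit monitoring to its listed conditions, so there is no outright contradiction, and that AST is the less liver-specific enzyme, so ALT alone could be deliberate. But the hold, the stopping criteria and the special-interest lists draw no such distinction, and no rationale is given.

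Lastly, Appendix 4 may name AST. It is not in the text available, so its content cannot be judged either way. The sentence that sends the investigator there still omits AST.

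**Conclusion.** The omission is real, and its practical reach is narrow. For an AST-led rise of > 3 to 5 × ULN with symptoms, eosinophilia above 5% or INR above 1.5 × ULN, a criterion for considering discontinuation is met with no compulsory hold and no 8.4.7 trigger. Above 5 × ULN only the hold applies. The remaining safeguards depend largely on the investigator's and medical monitor's judgement and do not specify the hepatic work-up that an ALT-led rise would start.

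This rests on reading 8.4.7 literally and on the visible text without Appendix 4. The number of patients affected cannot be estimated, because the protocol gives no frequency of such rises. No delay in days can be claimed either, since the visible 8.4.7 sets no retest interval even for ALT. It is a minor safety-consistency correction. Sample size, power, type I error and efficacy inference are untouched.

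**What to change.** In 8.4.7, replace the ALT condition with ALT or AST ≥ 3 × ULN, and confirm that Appendix 4 uses the same trigger. If ALT alone is intended, state that and the reason in one sentence.

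The edit adds two words. With it, every isolated AST rise at or above 3 × ULN starts the work-up, and the hold stays at > 5 × ULN. The cost is a few extra follow-up panels for AST rises of non-hepatic origin; creatine phosphokinase is already in the scheduled chemistry panel and helps to identify rises from muscle.
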